5.2. Exclusion Criteria

Participants are excluded from the study if any of the following criteria apply:

- 1. Known triggers for CHE (allergic or irritant, such as those identified by previous patch tests) cannot be avoided during the course of the study.
- 2. History of (within the past 5 years) or current AD or current psoriasis.
 - *Note*: Participants with CHE due to AD are not eligible.
- 3. Concurrent conditions and history of other diseases:
 - a. Other active skin disease or infection on the hands, including tinea manuum. In addition, foot eczema is excluded.
 - b. Immunocompromised (eg, lymphoma, acquired immunodeficiency syndrome, or Wiskott-Aldrich syndrome).
 - c. Chronic or acute infection requiring treatment with systemic antibiotics, antivirals, antiparasitics, antiprotozoals, or antifungals within 2 weeks before baseline.
 - d. Active acute bacterial, fungal, or viral skin infection (eg, herpes simplex, herpes zoster, chickenpox, or impetigo) within 1 week before baseline.
 - e. Any other concomitant skin disorder (eg, generalized erythroderma such as Netherton syndrome), pigmentation, or extensive scarring that in the opinion of the investigator may interfere with the evaluation of CHE lesions or compromise participant safety.
 - f. Unstable asthma or COPD requiring systemic treatment (such as intravenous steroids) or hospital admission or emergency department treatment within 3 months from baseline or stable asthma or COPD requiring budesonide more than 720 μ g/day (2 puffs BID of 180- μ g dose) or fluticasone more than 440 μ g/day (2 puffs BID of 110- μ g dose) or other equivalent high dose of other inhaled corticosteroids.
 - g. Current or history of hepatitis B or C virus infection.
- 4. Any serious illness or medical, physical, or psychiatric condition(s) that, in the investigator's opinion, would interfere with full participation in the study, including administration of study drug and attending required study visits; pose a significant risk to the participant; or interfere with interpretation of study data. For example:
 - a. Clinically significant or uncontrolled cardiovascular disease, including unstable angina, acute myocardial infarction, or stroke within 6 months from Day 1 of study drug application, New York Heart Association Class III or IV congestive heart failure, and arrhythmia requiring therapy or uncontrolled hypertension (blood pressure > 150/90 mm Hg) unless approved by the medical monitor/sponsor.
 - b. Participants with or a history of malignancy in the 5 years preceding the baseline visit, except for adequately treated nonmetastatic nonmelanoma skin cancer.
 - c. Current and/or history of arterial or venous thrombosis, including deep venous thrombosis and pulmonary embolism.
 - d. Current and/or history of active tuberculosis or current and/or history of latent tuberculosis unless adequately treated.
 - e. History of severe anemia, severe thrombocytopenia, or severe neutropenia.

- 5. Any of the following clinical laboratory test results at screening:
 - a. Cytopenias, defined as follows:
 - Hemoglobin $\leq 100 \text{ g/L}$ (ie, 10 g/dL)
 - Absolute neutrophil count $< 1.5 \times 10^9/L$ (ie, $1500/\mu L$)
 - Platelet count $< 1 \times 10^{11}/L$ (ie, $100,000/\mu L$)
 - b. Liver function tests:
 - AST or ALT ≥ 2.5 × ULN
 - Total bilirubin > 1.5 × ULN unless Gilbert syndrome
 - c. Estimated glomerular filtration rate < 30 mL/min/1.73 m² (using the Chronic Kidney Disease Epidemiology Collaboration 2021 Equation).
 - d. Positive serology test results at screening for HIV antibody.
 - e. Any other clinically significant laboratory result that, in the opinion of the investigator, poses a significant risk to the participant.
- 6. Use of any of the following treatments within the indicated washout period before the baseline visit:
 - a. 12 weeks or 5 half-lives, whichever is longer biologic agents (eg, dupilumab). For biologic agents with washout periods longer than 12 weeks (eg, rituximab), consult the medical monitor.
 - b. 4 weeks systemic corticosteroids or adrenocorticotropic hormone analogs; cyclosporine, methotrexate, azathioprine, or other systemic immunosuppressive or immunomodulating agents (eg, mycophenolate or tacrolimus); or oral alitretinoin or any other systemic treatment for CHE.
 - c. 4 weeks for any topical or systemic JAK or TYK2 inhibitor (eg, abrocitinib, baricitinib, brepocitinib, deucravacitinib, filgotinib, lestaurtinib, pacritinib, ruxolitinib, tofacitinib, upadacitinib).
 - d. 2 weeks or 5 half-lives, whichever is longer strong systemic CYP3A4 inhibitors.
 - e. 2 weeks systemic antibiotics, immunizations with live-attenuated vaccines, or sedating antihistamines unless on a long-term stable regimen (nonsedating antihistamines are permitted).
 - *Note:* Live-attenuated vaccines are not recommended during the DBVC period. COVID-19 vaccination is permitted.
 - f. 1 week use of any topical treatments for CHE (other than bland emollients, eg, Aveeno® creams, ointments, sprays, and soap substitutes), such as corticosteroids, calcineurin inhibitors, topical antipruritics (eg, doxepin cream), phosphodiesterase 4 inhibitors, coal tar (shampoo), topical antibiotics or antifungals, and antibacterial cleansing body wash/soap.
 - *Note:* Diluted sodium hypochlorite "bleach" baths are allowed as long as they do not exceed 2 baths per week and their frequency remains the same throughout the study.
- 7. Psoralen ultraviolet A or ultraviolet B therapy for CHE within 4 weeks before baseline.
- 8. Pregnant or lactating participants or those considering pregnancy during the period of their study participation.

- 9. History of alcoholism or drug addiction within 1 year before screening or current alcohol or drug use that, in the opinion of the investigator, will interfere with the participant's ability to comply with the administration schedule and study assessments.
- 10. Current treatment or treatment within 30 days or 5 half-lives (whichever is longer) before the baseline visit with another investigational medication or current enrollment in another investigational drug protocol.
- 11. Known allergy or reaction to any of the components of the study cream.
- 12. In the opinion of the investigator are unable or unlikely to comply with the administration schedule and study evaluations.
- 13. Committed to a mental health institution by virtue of an order issued either by the judicial or the administrative authorities.
- 14. Employees of the sponsor or investigator or otherwise dependents of them.

5.3. Lifestyle Considerations

Participants should be cautioned to avoid excessive exposure to artificial sunlight (including tanning booths, sun lamps, etc).

If sunscreen or other cosmetics have been applied to the areas to be treated, participants should follow the guidance in Section 6.6 regarding concomitant medications.

It is recommended that swimming should not take place within 2 hours before and after the planned study cream application.

Participants should not use hand sanitizer within 1 hour of study cream application. In addition, they should not wash or wet their hands or use hand sanitizer at a minimum within 1 hour after study cream application. In case of glove use, participants should ensure that the skin area where study cream is applied is completely dry before putting on glove(s).

5.4. Screen Failures

Screen failures are defined as participants who consent to participate in the clinical study but are not subsequently randomly assigned to study treatment.

Tests with results that fail eligibility requirements may be repeated once during screening if the investigator believes the result to be in error. Additionally, a participant who fails screening may repeat the screening process 1 time if the investigator believes that there has been a change in eligibility status. Participants who rescreen must reconsent and be assigned a new participant ID number.

5.5. Replacement of Participants

No participants will be replaced at any time during this study. However, as noted in the COVID-19—related guidance (see Appendix B), due to the evolving situation of the COVID-19 pandemic, the sponsor may decide to recruit additional participants in the study beyond the expected number (eg, if a substantial number of participants withdraw early from the study).

6. STUDY TREATMENT

6.1. Study Treatment Administered

Ruxolitinib 1.5% cream or matching vehicle cream will be applied as a thin film BID, with applications at least 8 hours apart in the morning and in the evening at least 1 hour before bedtime.

On the first clinic visit day and subsequent in-house clinic visits, participants should not apply the study cream at home. The first application of the study cream on the day of the clinic visit will be done at the clinic.

At the baseline visit, an estimate of the %BSA to be treated (including hands and wrists [if applicable]) will be used by the IRT system to calculate the number of tubes of study cream to be dispensed. The participant will apply a thin film of study cream in front of site staff at the baseline/Day 1 visit by applying study cream until all the affected areas to be treated are covered. All areas identified at baseline should continue to be treated through the end of the DBVC period (Week 16) unless the participant meets criteria for stopping study cream. If there are new areas to be treated on the hands and wrists, including expansion of existing areas or development of new areas, after consultation with the investigator, study cream should be applied to these areas in addition to the areas treated at baseline, and the percentage of BSA to be treated will be recalculated and increased. This new estimate will be entered into the IRT system to calculate the number of tubes of study cream to be dispensed.

During the OLE period starting at the Week 16 visit, CHE lesions will be evaluated by the investigator to confirm whether the participant still requires continuation of therapy (IGA-CHE score ≥ 1) or can otherwise (re)enter the observation/no treatment cycle (IGA-CHE score = 0). At Week 16, the IRT system will dispense a prespecified number of tubes according to the assessment of total BSA affected.

Between OLE study visits, participants will self-evaluate recurrence of CHE (if applicable) and will treat all areas identified with active changes. If all signs and symptoms of CHE resolve between study visits, participants will stop treatment applications 3 days after they have disappeared. If this 3-day window is during a study visit and the IGA score for CHE (if applicable) is 0, as assessed by the investigator, treatment is to be stopped at the study visit.

Participants will restart treatment of their CHE at the first sign of recurrence. In the event that new lesions are outside of the usual location and/or are more widespread than at baseline, the participant is required to contact the site for approval. Approval to treat additional areas may occur via telephone during the OLE period, although the investigator, at their discretion, may ask the participant to return for an unscheduled visit.

All tubes (including caps) of study cream will be weighed before being dispensed. All returned tubes (including caps) of study cream will also be weighed.

Application instructions will be provided by the site staff, and the participant will record their daily applications via eDiary. Refer to the Study Pharmacy Manual for participant instructions for handling study cream.

Table 5 presents the study treatment information.

Table 5: Study Treatment Information

	Study Treatment 1	Study Treatment 2			
Study treatment name:	Ruxolitinib	Vehicle			
Mechanism of action:	JAK 1/2 inhibitor	Not applicable			
Dosage formulation:	Cream	Cream			
Treatment strength:	1.5%	Not applicable			
Administration instructions:	DBVC period: Apply a thin film to affected areas identified at baseline in the morning and at least 1 hour before bedtime with applications at least 8 hours apart for 16 weeks. OLE period: Apply a thin film to affected areas in the morning and at least 1 hour before bedtime with applications at least 8 hours apart as needed for 16 weeks.				
Packaging and labeling:	Ruxolitinib or vehicle cream will be provided in 60-g tubes. Each tube will be labeled as required per country requirement.				
Storage:	15°C-30°C (59°F-86°F)				
Status of treatment in participating countries:	Investigational				

6.2. Preparation, Handling, and Accountability

The investigator or designee must confirm appropriate temperature conditions have been maintained during transit for all study treatments received and any discrepancies are reported and resolved before use of the study treatment.

Only participants enrolled in the study may receive study treatment, and only authorized site staff may supply study treatment. Participants should not wash their hands, if possible, within 1 hour after application of study cream. Refer to the Study Pharmacy Manual for participant instructions for handling of study cream.

All study treatment must be stored in a secure, environmentally controlled, and monitored (manual or automated) area in accordance with the labeled storage conditions with access limited to the investigator and authorized site staff. Participants should store study treatment at ambient temperature conditions.

The investigator (or designee) is responsible for study treatment accountability, reconciliation, and record maintenance (ie, receipt, reconciliation, and final disposition records). Inventory and accountability records must be maintained and readily available for inspection by the study monitor and are open to inspection at any time by any applicable regulatory authorities. The investigator or designee must maintain records that document the following:

- Delivery of study cream(s) to the study site.
- Inventory of study cream(s) at the site.

- Participant use of the study cream(s), including tube counts from each supply dispensed.
- Return of study cream(s) to the investigator or designee by participants.

The investigational product must be used only in accordance with the Protocol. The investigator or designee will also maintain records adequately documenting that the participants were provided the specified study cream. These records should include dates, quantities, and any available batch or serial numbers or unique code numbers assigned to the investigational product and study participants.

Completed accountability records will be archived by the site. The investigator or designee will be expected to collect and retain all used, unused, and partially used tubes of study cream until verified by the study monitor (unless otherwise agreed to by the sponsor). At the conclusion of the study, the investigator or designee will oversee the destruction of any remaining study drug according to institutional SOPs. If, however, local procedures do not allow on-site destruction, shipment of the study drug back to the sponsor is allowed. In this case, the site should (where local procedures allow) maintain the investigational supply until the study monitor inspects the accountability records in order to evaluate compliance and accuracy of accountability by the investigative site. At sites where the study cream is destroyed before monitor inspection, the monitors rely on documentation of destruction per the site SOP.

Further guidance and information for the final disposition of unused study treatments are provided in the study materials provided to the sites.

6.3. Measures to Minimize Bias: Randomization and Blinding

All participants will be centrally assigned to study treatment using an IRT system. The IRT system will assign in a 1:1 ratio, stratified by baseline IGA-CHE score (3 or 4) and region (North America or outside of North America), the participant study number, track participant visits, randomize according to the defined parameters, maintain the blinding, and manage study cream inventory. Full details will be provided in the IRT Manual.

Participants, investigators, and the sponsor will be blinded to each participant's treatment assignment during the DBVC period. During the OLE period, participants and investigators will remain blinded to the treatment assignment during the DBVC period. Emergency unblinding will occur if an AE requires the investigator to be made aware of the participant's treatment assignment (see emergency unblinding procedures in Section 9.7 and refer to the IRT Manual).

6.4. Study Treatment Compliance

Compliance with all study-related treatments should be emphasized to the participant by site personnel, and appropriate steps should be taken to optimize compliance during the study. Compliance will be assessed for frequency of administration of study cream by reviewing the participants' eDiaries. Participants will also be questioned regarding study cream application technique, missed applications, and use of any additional topical or systemic prescriptions of other products or over-the-counter products. Compliance with study cream will be evaluated by the participant's adherence to the BID application regimen (evaluation of actual number vs prescribed number of applications), documented by the site staff, and monitored by the sponsor/designee.

Qualified clinical staff will review the eDiary entries for compliance. Participants will be considered compliant with the treatment regimen if they apply at least 80% but no more than 120% of the prescribed number of applications during participation in the DBVC period of the study. Participants who are noncompliant during the DBVC period and OLE period (if on a treatment cycle) will be reinstructed by the investigator (or designee), and the sponsor should be consulted by the investigator for instruction on the proper handling of the participant.

Drug accountability will be assessed by documenting the quantities of drug used between study visits (tube counts and weighing). At the first clinic visit and subsequent study visits, all tubes (including caps) of study cream will be weighed before being dispensed and when returned. Participants will be instructed to bring all study cream with them to the study visits in order for site staff to assess study cream accountability.

6.5. Dose Modifications

There are no study drug application adjustments/modifications allowed (eg, frequency of application) except for drug interruption or permanent discontinuation if needed (eg, for management of an AE).

Temporary interruption could be due to an AE during the DBVC or OLE period (see Section 6.5.1) or clearance of the CHE during the OLE period, as described in Section 6.1.

6.5.2. Criteria for Permanent Discontinuation of Study Drug

The occurrence of unacceptable toxicity not caused by the underlying disease may require that the study drug be permanently discontinued. Unacceptable toxicity is defined as follows:

- The occurrence of an AE that is related to the study drug that, in the judgment of the investigator or the sponsor's medical monitor, compromises the participant's ability to continue study-specific procedures or is considered to not be in the participant's best interest.
- Worsening of CHE that requires treatment with a prohibited concomitant medication.
- An AE that requires an interruption of study drug for more than 2 weeks.
- Confirmed Grade 4 laboratory abnormalities related to study drug (see Section 6.5.1).

See Section 7 for discontinuation procedures.

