6.6.3. Prohibited Medications and Procedures

No rescue treatment or therapy is allowed during the study (see Section 6.5.2). In addition, the following are not permitted during the study:

- Any investigational medication other than the study drug.
- Treatment known to affect the course of CHE.
- Topical corticosteroids; topical calcineurin inhibitors; systemic corticosteroids (except short-term use of systemic corticosteroids to treat an AE during the OLE period, see Section 6.6.2); methotrexate, cyclosporin A, azathioprine and biological therapies, or other immunosuppressant agents; and oral alitretinoin or any other systemic treatment for CHE.
- Strong systemic CYP3A4 inhibitors.
- Phototherapy or tanning beds.
- Live-attenuated vaccination during the DBVC period.

Note: COVID-19 vaccination is permitted.

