7. DISCONTINUATION OF STUDY TREATMENT AND PARTICIPANT WITHDRAWAL

7.1. Discontinuation of Study Treatment

7.1.1. Reasons for Discontinuation

Participants **must** be discontinued from study treatment for the following reasons:

- Disease worsens requiring treatment with prohibited medication. The participant should be discontinued at the discretion of the investigator or based on discussions with the medical monitor.
- The participant becomes pregnant.
- Consent is withdrawn.

Note: Consent withdrawn means that the participant has explicitly indicated that they do not want to be followed any longer; in this case, no further data, except data in the public domain, may be solicited from or collected on the participant. Participants may choose to discontinue study treatment and remain in the study to be followed for disease progression and survival.

- Further participation would be injurious to the participant's health or well-being, in the investigator's medical judgment.
- Unacceptable toxicity as noted in Section 6.5.
- The study is terminated by the sponsor.
- The study is terminated by the local health authority, IRB, or IEC.

A participant **may** be discontinued from study treatment as follows:

- If, after 2 consecutive study visits and reinforcement of study drug application by site staff, a participant's drug usage exceeds one 60-g tube every 4 days; a participant who again fails to meet compliance benchmarks at a subsequent visit may be considered for withdrawal from the study. The medical monitor should be consulted for instruction on handling the participant.
- If, during the course of the study, a participant is found not to have met eligibility criteria, the medical monitor, in collaboration with the investigator, will determine whether the participant should be withdrawn from study treatment.
- If a participant is noncompliant with study procedures or study drug administration in the investigator's opinion, the sponsor should be consulted for instruction on handling the participant.

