10.4.1. Primary Analysis

The key parameters for the primary analysis are provided in Table 11. The primary analysis will be based on the ITT population. The primary alternative hypothesis (superiority of active ruxolitinib 1.5% cream BID compared with vehicle cream) will be tested at a 2-sided $\alpha = 0.05$ level using a Cochran-Mantel-Haenszel test stratified by IGA-CHE score (3 or 4) and region (North America or outside of North America). A summary of IGA-CHE-TS rates will be reported for each treatment group. The p-value and stratum-adjusted IGA-CHE-TS rate difference with 95% CI will be provided (Mantel and Haenszel 1959).

Table 11: Summary of Primary Analysis

Parameter	Definition
Treatment	Ruxolitinib 1.5% cream compared with vehicle cream
Population	ITT population
Variable	IGA-CHE-TS at Week 16: defined as an IGA-CHE score of 0 or 1 with ≥ 2-grade improvement from baseline
Population-level summary	Stratum-adjusted IGA-CHE-TS rate difference with 95% CI

All nonresponders in the DBVC period, participants who discontinue study treatment at any time before the timepoint of interest, and participants who discontinue from the study for any reason will be defined as nonresponders for the nonresponder imputation analysis. Subgroup analysis by baseline characteristic (eg, IGA-CHE, region, or age) will be performed.

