#### 6.3. Protocol Deviations

Protocol deviations will be summarized by treatment groups in the DBVC and OLE periods, separately.

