#### 7.3.2. Primary Efficacy Analyses

The key parameters for the primary analysis are provided in Table 4. The primary analysis will be based on the ITT population in the DBVC period. The primary alternative hypothesis (superiority of active ruxolitinib 1.5% cream BID compared with vehicle) will be tested at a 2-sided  $\alpha = 0.05$  level using a CMH test stratified by stratification factors IGA-CHE score (3 or 4) and region (North America or outside of North America). The p-value and overall odds ratio

with 95% CI will be provided. Summary of IGA-CHE-TS rates will be reported for each treatment group. Stratum-adjusted IGA-CHE-TS rate difference (1.5% BID vs vehicle) and 95% CI will be computed using Mantel-Haenszel weights (Mantel and Haenszel 1959).

**Table 4:** Summary of Primary Analysis

Parameter	Definition	
Treatment	Ruxolitinib 1.5% cream compared with vehicle cream	
Population	ITT Population	
Variable	IGA-CHE-TS at Week 16: Defined as an IGA-CHE score of 0 or 1 with ≥ 2 grade improvement from baseline	
Population-level summary	Stratum-adjusted IGA-CHE-TS rate difference with 95% CI	

All nonresponders during the DBVC period, as well as all participants missing Week 16 assessment and who discontinue study treatment at any time before Week 16, or discontinue from the study for any reason, will be defined as nonresponders for the nonresponder imputation analysis.

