## 7.4.2. Key Secondary Efficacy Analysis

Key secondary efficacy analyses will be conducted in the ITT population in the DBVC period. If the primary objective is achieved, the statistical comparisons for key secondary endpoints will be tested with the procedures specified in Section 3.2. The same nonresponder imputation method as specified in the primary analysis will be used to handle missing Week 4 and Week 16 itch data.

For the key secondary endpoints of ITCH4 at Week 1 (Day 7), all participants who are missing Day 7 daily Itch NRS scores will be imputed using multiple imputation by fully conditional specification method. The variables to be included in the imputation regression model are treatment group, stratification factor, baseline itch score, and postbaseline daily itch score on Day 1 to Day 7. The corresponding binary response on Day 7 will be derived for each of the imputed datasets per the definition in Section 7.4.1.1.

The following sample SAS code will be used for the MI:

```
proc mi data=mi_wide seed=18424226 nimpute=30 out=impute_itch;
class trt01p strat1 strat2;
var trt01p strat1 strat2 base avald1 avald2 avald3 avald4 avald5
avald6 avald7;
fcs regpmm nbiter=30;
run;
```

All key secondary efficacy analyses will use stratified CMH test similar to the primary efficacy analysis. The summary of key secondary endpoints analysis is also provided in Table 5.

**Table 5:** Summary of Analyses for Key Secondary Endpoints

Parameter	Definition	
Treatment	Ruxolitinib 1.5% cream compared with vehicle cream	
Population	ITT population	
Variables	ITCH4 response at Week 16 ITCH4 response at Week 4 ITCH4 response at Week 1 (Day 7)	
Population-level summary	Stratum-adjusted IGA-CHE-TS rate difference with 95% CI	

Note 1: Participants with missing observed data at the timepoint of interest (Week 4, Week 16), participants who discontinue study treatment at any time before the timepoint of interest (Week 4, Week 16), and participants who discontinue from the study for any reason will be defined as nonresponders. Participants with missing observed data at Day 7 will be imputed using multiple imputation by fully conditional specification method. No rescue therapy or treatment switch is allowed in this study. Note 2: ITCH4 is defined as  $a \ge 4$ -point improvement in CHE-related Itch NRS score from baseline.

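### Stopping for eczema worsening that needs a prohibited drug is worded inconsistently, and no nonresponder rule says how a participant who takes such a drug and stays on cream is scored

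*Protocol*

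**What the plan says.** **Stopping.** Protocol 6.6.3 bans rescue and prohibits, among others, topical and systemic corticosteroids, topical calcineurin inhibitors, other immunosuppressants, alitretinoin and phototherapy. It refers to 6.5.2 for rescue. Section 6.5.2 includes "Worsening of CHE that requires treatment with a prohibited concomitant medication" in its definition of unacceptable toxicity, and its opening sentence says such toxicity "may require that the study drug be permanently discontinued". Section 7.1.1 has a list of reasons for which treatment *must* stop. Its first entry reads "Disease worsens requiring treatment with prohibited medication. The participant should be discontinued at the discretion of the investigator", or on discussion with the medical monitor. A later entry in the same list is unacceptable toxicity as described in Section 6.5.

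**Scoring.** Protocol 10.4.1 counts as nonresponders those with observed nonresponse, "participants who discontinue study treatment at any time before the timepoint of interest, and participants who discontinue from the study for any reason". SAP 7.3.2 also names "all participants missing Week 16 assessment and who discontinue study treatment at any time before Week 16", which I read as separate conditions. For ITCH4 at Weeks 4 and 16, SAP Table 5 Note 1 lists missing data, treatment discontinuation and study discontinuation, and adds "No rescue therapy or treatment switch is allowed in this study". On departures from the Protocol, SAP 6.3 says "Protocol deviations will be summarized by treatment groups in the DBVC and OLE periods, separately".

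**The concern.** The plan treats stopping study cream as failure. Whether a participant stops after needing a prohibited drug is not worded consistently, so two sites could handle the same event differently and produce different primary endpoint values. The prohibited drugs include active eczema treatments, so a Week 16 score of 0 or 1 in a participant kept on cream could owe something to the other drug.

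The scoring gap also exists without any site decision. A participant may use a leftover steroid cream unprompted, continue the study cream and attend Week 16. Noncompliance with study procedures is only an optional ground for stopping in 7.1.1. The same rule feeds ITCH4 at Weeks 4 and 16, and the primary endpoint is the gate to all three ITCH4 tests.

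**Working it through.** **1. Is stopping mandatory?**

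| Place | Force of the wording for this event |
|---|---|
| Protocol 7.1.1, first entry | Mandatory heading, discretionary sentence |
| Protocol 7.1.1, toxicity entry, pointing to 6.5 | Mandatory, no discretion wording |
| Protocol 6.5.2, opening sentence | Optional (may) |
| Protocol 6.6.3 | Bans rescue, refers to 6.5.2 |

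Mandatory stopping is stated by two routes and softened in two places. Section 6.5.1 is not in the public text, but the visible sections cite it only for adverse-event interruptions and Grade 4 laboratory values.

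**2. How is each participant scored at Week 16?** Take a participant who worsened and started a prohibited eczema drug before Week 16.

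| Course | Score under the present rules |
|---|---|
| Stops cream or leaves the study | Nonresponder |
| Stays on cream, Week 16 missing | Nonresponder (SAP 7.3.2) |
| Stays on cream, observed nonresponse | Nonresponder |
| Stays on cream, observed IGA-CHE-TS | **Responder** |

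Only the last row is at issue. The populations in Protocol 10.2 and SAP 5.3 include no per-protocol set. The IGA-CHE-TS tables in SAP Appendix A are observed, nonresponder-imputed and subgroup tables, and none isolates prohibited use.

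**3. The plan's own figure.** Inputs from Protocol 10.1: 90 per arm, 26% vs 10%, chi-square test, 2-sided α 0.05.

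- SE₀ = √(2 × 0.18 × 0.82 / 90) = 0.0573, where 0.18 is the mean of the two rates
- SE₁ = √((0.26 × 0.74 + 0.10 × 0.90) / 90) = 0.0560
- Power = Φ((0.16 − 1.96 × 0.0573) / 0.0560) = 80.3%, against 80% stated

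**4. Illustration of size.** The documents give no frequency, so every count below is an assumption. Suppose 26% and 10% hold when such users count as nonresponders. Let k participants in an arm start a prohibited eczema drug and stay on cream, and let a proportion r of them reach IGA-CHE-TS. Under the present rules that arm's rate becomes planned rate + k × r / 90. I take r from 10% (the planned vehicle rate) to 40%, with the same range of k in both directions.

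| k vehicle / k ruxolitinib | Difference, r = 10% to 40% | Power, r = 10% to 40% |
|---|---|---|
| 0 / 0 | 16.0 | 80.3% |
| 3 / 1 | 15.8 to 15.1 | 78.8% to 74.0% |
| 9 / 3 | 15.3 to 13.3 | 75.6% to 60.0% |
| 3 / 3 | 16.0 | 79.7% to 78.1% |
| 9 / 9 | 16.0 | 78.6% to 74.0% |
| 1 / 3 | 16.2 to 16.9 | 81.0% to 83.1% |
| 3 / 9 | 16.7 to 18.7 | 82.4% to 87.8% |

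Example, 9/3 with r = 40%: vehicle 10 + 9 × 0.4 / 90 = 14.0%; ruxolitinib 26 + 3 × 0.4 / 90 = 27.3%; difference 13.3 points. Heavier use on vehicle shrinks the difference and heavier use on ruxolitinib enlarges it. The table shows sensitivity and is not a forecast.

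**The case against.** - **Stopping is mandatory after all.** This has weight. The toxicity entry in 7.1.1 reaches the event through 6.5.2 with no discretion attached. The discretion sentence can also be read as discretion over whether the worsening requires prohibited medication. Where the Protocol does contemplate keeping someone after systemic steroids (6.6.2), it says so, and only for acute adverse events in the open-label period. A reader might infer that the Protocol leaves continuation wholly open. The text supports only inconsistent wording.
- **The case is narrow.** True. A reader might infer that the nonresponder rules catch only participants who stop. They also catch observed nonresponse and, in the SAP, missing data. What remains is an observed success after prohibited treatment in someone still on cream.
- **The ban settles it.** It does not. A ban says what should not happen, not how the result is scored if it does. Protocol 6.4 has sites ask about additional prescription and over-the-counter products, so such use is foreseen.
- **Scoring on the observed value is legitimate in an intent-to-treat analysis.** It is, but the plan would have to say so. The plan already counts stopping as failure, so counting prohibited treatment as failure is the consistent extension.
- **The power figures are speculative.** Agreed. Nothing in the documents supports any particular k or r.

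**Conclusion.** The point holds as a wording inconsistency and a gap in the endpoint definition. For the same event, a participant who stops is a nonresponder, and one who stays on cream with an observed Week 16 success is a responder. Recording medications and summarizing deviations do not change either score.

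The size and direction are unknown. A reader might infer from the calculation that the trial is underpowered or its treatment difference biased. The documents do not support that: the stated power reproduces, the usage counts are assumed, the effect can go either way, and it vanishes if no one uses such a drug. This is a cheap clarification worth making before lock, not a threat to the design.

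**What to change.** **SAP 7.3.2, and Table 5 Note 1 for ITCH4 at Week 4 and Week 16.** Add to the nonresponder definition:

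> or who start a topical corticosteroid, topical calcineurin inhibitor, systemic corticosteroid or other immunosuppressant, alitretinoin, phototherapy, or other treatment known to affect CHE that is prohibited by Protocol 6.6.3, before the timepoint, whether or not study treatment is stopped.

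Identify users by blinded review of the eCRF concomitant medications before the primary database lock. Naming the treatments keeps out prohibited items listed for other reasons, such as live vaccines. If the rule is also applied to ITCH4 at Day 7, set these users to nonresponse after the multiple imputation, so that the two rules do not conflict.

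**Protocol.** The SAP clause settles the scoring by itself. The discretion sentence in 7.1.1 can be aligned at the next amendment, for this criterion only, so that judgment applies to whether prohibited medication is required and not to whether treatment then stops. Leave 6.5.2 unchanged for its other three criteria, on which this point makes no claim. An amendment solely for this is not warranted, since Protocol 11.1 requires health-authority and IRB/IEC approval.

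**Cost.** One SAP clause in two places and a short blinded medication review. No new visits, data or sample size. Response rates may be slightly lower.
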